#### Main Study: Randomization

Only subjects meeting the inclusion and exclusion criteria during the screening visit will be randomized. Subjects will be assigned to receive placebo x 4 doses on the first day of GH stimulation testing and niacin 500 mg x 4 doses on the second day or they will be assigned to receive niacin 500 mg x 4 doses on the first day and placebo x 4 doses on the second day. Subjects

will be stratified by group and sex in blocks of 4 such that roughly equal numbers of subjects in each stratum will be assigned to each placebo and active medication administration order.

Additionally randomization of obese subjects will be stratified by BMI (95-99th percentile or >99th percentile).

Main Study: Inpatient evaluation:

Only subjects meeting the inclusion and exclusion criteria during the screening visit will be evaluated as inpatients. A total of 40 subjects in the two main groups will complete inpatient evaluation, although up to 50 may initiate inpatient evaluation in order to achieve full enrollment. The inpatient visit will occur within two months of screening visit to ensure consistency of physical exam and medical history throughout the study period. Patients will be admitted the night before the first day of testing. Additionally, literature suggests that several vitamins influence growth hormone secretion; thus, if applicable, vitamin supplements will be discontinued for three days prior to admission. All subjects will be admitted to the NIH Clinical Center for an evaluation that will include:

1. **Medical History and Physical Examination** with Tanner pubertal staging and anthropometric measurements including weight (in kg) and height (in cm) by stadiometer (3 repeated measures).
2. **DXA scanning** for determination of lean body mass and body fat mass.
3. **Placement of an intravenous line** to be used for medication administration and blood sampling over a 48 hour time period.
4. **Repeat urine pregnancy test** in girls age 10 and older.
5. **Overnight Fast** beginning at 10 pm on both nights; ending after completion of testing each day.
6. **Growth Hormone Stimulation testing** consisting of arginine (500 mg/kg IV up to maximum of 30 g, infused over 30 min) at 8:30am, followed by L-dopa (500 mg by mouth)

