### **Data Analysis**

Primary research outcome will be niacin-induced changes in arginine and L-dopa stimulated GH concentrations, measured as both area under the curve and peak values, in the overweight group compared with the control group. Secondary research outcomes will include changes in free fatty acid, glucose, and insulin concentrations during the GH stimulation tests. Since non-completion of the study is expected to be due to technical failures (e.g., nonfunctioning IVs) rather than subject factors, all analyses will be limited to subjects who complete both placebo and niacin studies. We do expect that some members of the control group will not reach a peak GH concentration of 7 ng/mL during the stimulation testing. We will report all control subjects in the final analyses. Analyses will be performed with age, Tanner stage, and initial BMI-SDS as covariates. Furthermore, tertiary analyses will also be performed to compare subjects in the Tanner I, Tanner II, and Tanner III groups to determine if any differences exist among these pubertal development stages. This analysis will be for exploratory purposes only; the study is not powered for this subgroup analysis. Additionally if any members of the control group have abnormally elevated lipid levels, we will specifically examine these subjects and their growth hormone concentrations. The primary outcome analysis will therefore be a repeated measures ANCOVA with subject group (obese and control) as the between factor, treatment (niacin or placebo) as the repeated measure, GH concentration (peak and AUC) as the outcome variables, and age, sex, and Tanner pubertal stage as covariates. We will also model the subject group by treatment interaction but no other interaction terms will be entered into the primary analysis.

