### **Limitations to the Study Design**

**We have identified several possible limitations to our study, including:**

- 1) Given that the GH stimulation tests are being performed on consecutive days, it is possible that effects of the first day's testing could carry-over to the second day and affect the results. However, many studies in the adult literature have used similar study designs. Furthermore, Cavallo et al showed no difference in response to GH stimulation testing on two consecutive days. Additionally, by randomizing the order of placebo or niacin given during the stimulation tests, we believe any effects of order will be detected.
- 2) Niacin is known to cause flushing shortly after administration. We anticipate that this side effect may conceivably lead the subjects and investigators to become aware of which day the niacin and placebo capsules were administered. We do not believe the blinding is critical to the success of the study given that we are only measuring objective hormonal data.

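### The crossover's primary model has no test-day term and no listed analysis looks at order, so the protocol's assurance about order effects rests on no analysis

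*Combined protocol and SAP*

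**What the plan says.** Each child has two stimulation tests on consecutive days, one with niacin and one with placebo, in random order. Main Study: Randomization stratifies in blocks of 4 so that "roughly equal numbers of subjects in each stratum will be assigned to each placebo and active medication administration order".

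The Data Analysis section defines the primary model as a repeated measures ANCOVA "with subject group (obese and control) as the between factor, treatment (niacin or placebo) as the repeated measure". The covariates are age, sex and Tanner stage; another sentence in the section lists age, Tanner stage and BMI-SDS. It adds: "We will also model the subject group by treatment interaction but no other interaction terms will be entered into the primary analysis". The other analyses listed are changes in FFA, glucose and insulin, an exploratory comparison ("tertiary analyses will also be performed to compare subjects in the Tanner I, Tanner II, and Tanner III groups"), and a look at any control children with raised lipids. The analysis set is restricted: "all analyses will be limited to subjects who complete both placebo and niacin studies".

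Limitations to the Study Design, item 1, concedes that "it is possible that effects of the first day's testing could carry-over to the second day and affect the results". It replies with a cited study that "showed no difference in response to GH stimulation testing on two consecutive days", and with the statement that "by randomizing the order of placebo or niacin given during the stimulation tests, we believe any effects of order will be detected".

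**The concern.** The Limitations section depends on an analysis that the Data Analysis section does not contain. Randomising the order protects the treatment estimate from a day shift on average. Seeing whether a shift occurred requires fitting or testing day or order, and no listed analysis does so.

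The sentence on interactions makes this harder to settle. It does not mention a main effect of day, so a day term might be allowed. But in a two-period crossover coded by sequence, the day effect is the sequence-by-treatment interaction, which the sentence would exclude.

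Two things are at stake. If the second day's response differs from the first, that difference stays in the residual and widens the intervals in a study of 40 children. And the trial would not show whether the cited finding of no consecutive-day difference holds in these children.

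**Working it through.** **Does any analysis cover day or order?** Setting the sections side by side: the primary model has group, treatment, their interaction and baseline covariates; the secondary, exploratory and lipid analyses add nothing on day, period or sequence. The Introduction's overview of the study and the two randomisation sections deal with order by design only.

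**Is there a figure in the plan to reproduce?** Not for a day effect. The sample-size section supplies the scale: an increase of 10.3 µg/L with SD 6.1, a 10 µg/L difference to detect, 14 per group for power 0.80 and 22 for 0.95, and a target of 20 completers per group. With a two-sided two-sample t test, SD 6.1 gives 7 and 11 per group, not 14 and 22. SDs of about 8.8 to 9.0 fit both stated figures. I therefore used two SDs for the within-child change: 6.1 (the quoted value read as the SD of the change) and 9.0 (the value implied by the stated sample sizes).

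**Set-up.** Let π be the Day 2 minus Day 1 shift common to all children and τ the child's group's niacin effect. The niacin-minus-placebo change has mean τ + π if niacin is given on Day 2 and τ − π if on Day 1. Baseline covariates entered without treatment interactions cancel from this change. The group-by-treatment test is therefore a two-sample t test on the change (38 df) without a day term, or a regression on group and order sign (37 df) with one. The documents give no π; 0, 1, 3 and 5 µg/L are assumptions.

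**Orders balanced 10:10 in each group.**
- The true sampling SD of the contrast is 6.1 × √(2/20) = 1.93 whatever π is, because the shift cancels.
- The estimated error does not cancel it. The expected pooled variance is SD² + π² × 40/38. At π = 3 this is 37.21 + 9.47 = 46.68, root 6.83. The half-width is about 2.024 × 6.83 × √(2/20) = 4.37, against 2.024 × 6.1 × √(2/20) = 3.90 at π = 0.

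Simulation without a day term (100,000 trials or more per case, two-sided 0.05):

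| SD | π (µg/L) | Mean 95% CI half-width | Type I error | Power at 10 µg/L | Power at 5 µg/L |
|---|---|---|---|---|---|
| 6.1 | 0 | 3.88 | 0.049 | 0.999 | 0.711 |
| 6.1 | 1 | 3.93 | 0.048 | 0.999 | 0.704 |
| 6.1 | 3 | 4.35 | 0.030 | 0.998 | 0.628 |
| 6.1 | 5 | 5.08 | 0.011 | 0.993 | 0.487 |
| 9.0 | 0 | 5.72 | 0.050 | 0.929 | 0.40 |
| 9.0 | 3 | 6.05 | 0.038 | 0.912 | 0.36 |
| 9.0 | 5 | 6.59 | 0.025 | 0.878 | 0.30 |

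With a day term, at SD 6.1 and every π shown, the half-width is 3.88, type I error 0.049 to 0.052 and power at 5 µg/L 0.711 to 0.717. At SD 9.0, power at 10 µg/L is 0.928 to 0.929.

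**Orders unequal among completers.** Without a day term, the contrast is shifted by π times the between-group difference in mean order sign. A 12:8 split in one group and 8:12 in the other gives 0.2 − (−0.2) = 0.4, so 1.2 µg/L at π = 3. To see what is likely, I simulated 20,000 trials: 25 per group, four obese and two control strata of random size, blocks of 4, five random losses per group.
- Both groups were exactly balanced in 11% of trials. The absolute shift had median 0.1π and 90th percentile 0.3π (0.9 µg/L at π = 3), and reached 0.4π or more in 3.7%.
- The mean bias was about zero. At SD 6.1 and π = 0, 3, 5 the sampling SD was 1.92, 2.00, 2.10 without the day term and 1.92 to 1.95 with it. Type I error without the term was 0.048, 0.036, 0.018.

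**What a day term could detect.** The 95% CI half-width for π is 2.03 × SD/√40, which is 1.95 µg/L at SD 6.1 and 2.9 at SD 9.0. With 40 completers split 20/20 by order and SD 6.1, power to detect a shift of 1, 2, 3 or 4 µg/L is 17%, 52%, 86% or 98%.

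**The case against.** The strongest reply is that little harm follows. The estimate is unbiased in expectation and the test errs on the conservative side, so a positive result is no less trustworthy. At the planned 10 µg/L and SD 6.1 the power loss is under one point even at π = 5. The larger losses need a shift of 3 to 5 µg/L, which no document supports, while the only evidence offered, the cited study, points to no shift. The steepest fall (0.71 to 0.49) also needs a 5 µg/L target that is not in the plan. At SD 9.0 the interval widens by 6% and 15% at π = 3 and 5, against 12% and 31% at SD 6.1. Finally, the sentence is a hedged remark under Limitations, and a day term cannot isolate carry-over specific to niacin.

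Most of this stands and limits the weight of the point. It does not supply the missing analysis. An assumption taken from another study is best checked in these children, and the data to check it are already collected. The limits on what a day term can detect are a reason to correct the sentence as well as the model.

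**Conclusion.** The point holds and should be fixed. The omission is certain from the text: no day or order term appears in any listed analysis, so the Limitations statement is unsupported. Its numerical effect depends on an unknown shift. It is negligible at 1 µg/L. At 3 to 5 µg/L it means a half-width 12% to 31% larger at SD 6.1 (6% to 15% at SD 9.0) and a loss of about 2 to 5 points of power at 10 µg/L if the SD is about 9.0. Averaged over randomisation there is neither bias nor excess false positives; a chance order imbalance can move the estimate in a single trial. These figures assume 20 completers per group, a shift common to all children, and normally distributed changes.

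**What to change.** 1. In Data Analysis, add test day (1 or 2) as a fixed within-subject effect in the primary model. State that the restriction on interaction terms does not exclude it, however it is coded.
2. Report the day estimate with its 95% confidence interval.
3. In Limitations, item 1, replace the assurance about order. Say that the day term estimates and adjusts for a shift common to all children, with limited precision, and that carry-over specific to niacin cannot be separated from sequence effects in this two-period design.

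The cost is two or three sentences and one degree of freedom (38 to 37). Test day is already recorded. If there is no shift, power is the same with or without the term (0.999 at 10 µg/L and 0.711 at 5 µg/L, SD 6.1).

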### **Determination of Sample Size**

Using data from the available studies that used acipimox, we performed power calculations based on the difference in effect on peak GH secretion found with and without use of acipimox in

obese adults. Following acipimox, this cohort showed an increase of 10.3 micrograms per liter in peak GH concentrations with a standard deviation of 6.1. Thus, at a power of .80 and an alpha of .05, the sample size necessary to detect a 10 microgram per liter difference in GH secretion is 14 in each group (e.g. obese versus control), and at a power of .95 and an alpha of .05, the sample size necessary to detect a 10 microgram per liter difference in GH secretion is 22 in each group. Given these calculations, we will aim for 20 subjects per group who complete all aspects of the study.

Allowing for 20% of subjects to fail to complete the main study for various reasons, the total number of subjects needed to be studied is 50 (25 in each group). We expect that we will need to screen no more than 66 children to find the 50 who meet the inclusion and exclusion criteria. Subjects will be randomized with the assistance of the NIH Investigational Drug Management and Research Section (IDMS); we anticipate sex and race/ethnicity to be similar in each study arm. For the pilot dose-finding studies, we will study no more than 5 per group (15 total) and screen at most an additional 10 subjects who do not qualify for these studies.

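### The 14 and 22 per group do not follow from the stated difference and SD, which give 7 and 11, and no control response is stated for the between-group primary contrast

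*Combined protocol and SAP*

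**What the plan says.** Determination of Sample Size takes its effect from studies of obese adults, namely the "difference in effect on peak GH secretion found with and without use of acipimox". The figures given are: "Following acipimox, this cohort showed an increase of 10.3 micrograms per liter in peak GH concentrations with a standard deviation of 6.1". From these it concludes that at 80% power and alpha 0.05 "the sample size necessary to detect a 10 microgram per liter difference in GH secretion is 14 in each group", with obese versus control given as the example of the groups. At 95% power the "sample size necessary to detect a 10 microgram per liter difference in GH secretion is 22 in each group". It then states that "we will aim for 20 subjects per group who complete all aspects of the study". It names no test and does not say whether alpha is one- or two-sided.

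Data Analysis defines the primary outcome as the niacin-induced change in stimulated GH, "measured as both area under the curve and peak values", "in the overweight group compared with the control group". The model is a repeated-measures ANCOVA with group as the between factor and treatment as the repeated factor. It includes the group-by-treatment term, and "no other interaction terms will be entered into the primary analysis".

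On the control group, Specific Hypotheses and the Overview of proposed pilot study both predict that niacin will raise GH in controls too. No section gives a size for that rise.

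**The concern.** There are two problems in the same paragraph.

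First, the sentence attaches the SD of 6.1 to the increase. A difference of 10 against an SD of change of 6.1 is a standardised effect of 10/6.1 = 1.64, which needs far fewer than 14 or 22 per group. A reader who takes the paragraph at its word will place 20 per group between 80% and 95% power for 10 µg/L, which is not what its inputs imply.

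Second, the 10 µg/L is a change within obese subjects, while the primary contrast is a difference between two groups' changes. If the obese rise is 10.3, a between-group difference of 10 needs a control rise of about 10.3 − 10 = 0.3 µg/L. The protocol's own hypotheses expect more than that. If controls respond well, the between-group comparison can be null while niacin works in both groups. That result would fit the within-group predictions, yet could be read as a failed primary outcome. The paragraph gives no warning of this. It also sizes peak GH only, although AUC is primary as well.

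**Working it through.** **Inputs.** From Determination of Sample Size: difference 10 µg/L, obese rise 10.3, SD 6.1, alpha 0.05, power 0.80 and 0.95, 20 completers per group. Assumed: normally distributed changes and equal SDs in the two groups. The test is taken as two-sided unless noted.

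**Formula.** For a two-sample t-test on niacin-minus-placebo changes with n per group, power = P(|T| > t(0.975, 2n−2)), where T is noncentral t with 2n−2 degrees of freedom and noncentrality 10 / (SD × √(2/n)).

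**Attempt to reproduce 14 and 22, SD 6.1.**

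| Test | n for 80% | n for 95% |
|---|---|---|
| Two-sample, two-sided | 7 (power 0.804) | 11 (power 0.955) |
| Two-sample, one-sided | 6 | 9 |
| Paired, two-sided | 6 | 8 |

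Using 10.3 in place of 10 still gives 7 and 11 for the two-sided two-sample test. That test's totals are 2 × 7 = 14 and 2 × 11 = 22, exactly the printed figures. At SD 6.1, 14 per group has 98.7% power and 20 per group has 99.9%.

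**Alternative reading.** Suppose 6.1 is the SD of a single test and the two days are uncorrelated. The SD of the change is then 6.1 × √2 = 8.63. The two-sided two-sample t-test needs 13 and 21 (unrounded 12.72 and 20.35). Dividing by 0.955 for a rank test gives 13.32 and 21.31, which round up to 14 and 22. At this SD, 20 per group has 94.6% power for 10 µg/L. Without a rank allowance, the t-test returns both 14 and 22 only for an SD of about 8.77 to 8.99, which appears nowhere in the protocol.

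**What 20 per group can detect at 80% power.**

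| | SD of change 6.1 | SD of change 8.63 |
|---|---|---|
| Between-group difference in change | 5.55 µg/L | 7.84 µg/L |
| Within-group change (paired) | 4.03 µg/L | 5.70 µg/L |

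With an obese rise of 10.3, the between-group test therefore keeps 80% power up to a control rise of 10.3 − 5.55 = 4.75 µg/L, or 10.3 − 7.84 = 2.46 µg/L.

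**Dependence on the control rise.** The protocol gives no value, so the range below is assumed. The obese rise is 10.3 with 20 per group. The joint event is that both within-group paired tests are significant while the interaction is not (100,000 simulated trials).

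| Control rise (µg/L) | Interaction power, SD 6.1 | Interaction power, SD 8.63 | Joint event, SD 6.1 | Joint event, SD 8.63 |
|---|---|---|---|---|
| 0 | 99.9% | 96% | <0.1% | 1% |
| 2 | 98.7% | 84% | 1% | 7% |
| 3 | 96% | 74% | 4% | 16% |
| 4 | 89% | 61% | 11% | 29% |
| 5 | 76% | 47% | 23% | 45% |
| 7 | 39% | 22% | 62% | 76% |

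**The case against.** The strongest case for the plan has four parts.

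- **Another reading recovers the figures.** An SD of change of 8.63 plus a rank-test allowance gives 14 and 22, the paragraph names no test, and the acipimox source cannot be seen. This stands as a possibility. It needs two assumptions the paragraph does not state, and it goes against the wording, which ties 6.1 to the increase. It is a reason to let the sponsor justify a different SD. It does not make the figures follow from the inputs given.
- **Nothing depends on the error.** This is correct for enrolment: 20 per group is ample for 10 µg/L on either reading.
- **The planned model also contains a treatment effect.** If both groups rise, the treatment main effect will show it. With 40 completers its power is at least 99.9% (SD 6.1) or 95.7% (SD 8.63) at every control rise tabulated, so a null interaction could be interpreted. This is a fair point. However, the primary outcome is worded as a comparison between groups, and the main effect does not power that.
- **The control rises are assumed, and zero correlation between days is extreme.** Both are true. At a correlation of 0.5, a single-test SD of 6.1 gives an SD of change of 6.1 again. A small control response also has some support: Effects of inhibiting lipolysis and Justifications for exclusions both describe a paediatric acipimox study without a significant rise after L-dopa. Against that, the title of the same study (reference 86) says acipimox stimulates GH secretion in short children, and the protocol's own hypotheses predict a rise.

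**Conclusion.** The concern holds and is minor. As written, 14 and 22 per group do not follow from a difference of 10 and an SD of 6.1; the two-sample t-test gives 7 and 11. A total mislabelled as a per-group number would explain the figures, but the text does not prove it. The error is conservative, so the trial is not underpowered for a true 10 µg/L difference.

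The missing control response matters somewhat more. The quoted power carries over to the primary contrast only if the obese rise is about 10.3 and the control rise is near zero. At SD 6.1, small control rises do little harm: power is still 89% at a rise of 4. At SD 8.63 it is already 74% at a rise of 3. The reproduction failure rests only on the stated inputs and standard tests. The size of the second problem rests on assumed control rises, equal SDs and normal changes.

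**What to change.** Keep 20 completers per group and reword the one paragraph:

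- Name the test and its sidedness, and say whether 6.1 is the SD of the change.
- Replace 14 and 22 with 7 and 11 per group (14 and 22 in total), or justify another SD and recalculate.
- Add text such as: *Twenty completers per group give 80% power for a between-group difference in niacin-induced change in peak GH of about 5.6 µg/L, and for a within-group change of about 4.0 µg/L (SD of change 6.1; 7.8 and 5.7 if it is 8.63). Power for the group-by-treatment contrast depends on the control response, for which no estimate is available. A null interaction does not by itself count against a niacin effect within either group. AUC was not included in this calculation.*

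The cost is one rewritten paragraph, with no change to enrolment, procedures or the analysis model.

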### **Pharmaceutical information**

#### **Packaging and Labeling:**

Niacin will be purchased from Upsher-Smith Laboratories, Inc, as 500 mg tablets, USP, that have been manufactured according to GMP. Each table contains 500 mg of nicotinic acid. In addition, each tablet contains the following inactive ingredients: croscarmellose sodium, hydrogenated vegetable oil, magnesium stearate and microcrystalline cellulose. From 2011-2016, niacin, and the niacin placebo were packaged, supplied, and distributed to the inpatient staff by the NIH pharmaceutical development section. The study was placed on hold when use of all PDS-prepared compounds was quarantined in December 2016. Afterwards, starting in mid- 2017, all study compounds will be prepared following the same procedures by Pine Pharmaceuticals. The niacin study medication will be packaged as 250 mg capsules using a Swedish orange/caramel

opaque #1 capsule. The same capsule components used for the niacin will be used for the placebo.

From 2011-2016 PDS, and subsequently, Pine Pharmaceuticals, supplies inert placebo capsules that match the weight of the unlabeled niacin capsules. Pine Pharmaceuticals will perform bioburden testing per the United States Pharmacopeia (USP) <61> and <62> standards. Purity and stability testing will be performed by the NIH Investigational Drug Management and Research Section. Labels for medication will be computer generated by the NIH CRIS system.

